10.3.2 Contraception Guidance

• CONTRACEPTIVES^a ALLOWED DURING THE STUDY INCLUDE:

- Highly Effective Methods^b That Have Low User Dependency Failure rate of <1% per year when used consistently and correctly.
- Implantable progestogen-only hormone contraception associated with inhibition of ovulation^b
- Intrauterine device
- Intrauterine hormone-releasing system ^b
- Bilateral tubal occlusion
- Azoospermic partner (vasectomized or due to a medical cause)

Azoospermia is a highly effective contraceptive method provided that the partner is the sole sexual partner of the woman of childbearing potential and the absence of sperm has been confirmed. If not, an additional highly effective method of contraception should be used.

Note: documentation of azoospermia for a male participant can come from the site personnel's review of the participant's medical records, medical examination, or medical history interview.

- **Highly Effective Methods**^b **That Are User Dependent** *Failure rate of* < 1% *per year when used consistently and correctly.*
- Combined (estrogen- and progestogen-containing) hormonal contraception associated with inhibition of ovulation^c
 - oral
 - intravaginal
 - transdermal
 - injectable
- Progestogen-only hormone contraception associated with inhibition of ovulation^c
 - oral
 - injectable
- Sexual abstinence

Sexual abstinence is considered a highly effective method only if defined as refraining from heterosexual intercourse during the entire period of risk associated with the study intervention. The reliability of sexual abstinence needs to be evaluated in relation to the duration of the study and the preferred and usual lifestyle of the participant.

- Effective Methods^d That Are Not Considered Highly Effective Failure rate of ≥ 1% per year when used consistently and correctly.
- Progestogen-only oral hormonal contraception where inhibition of ovulation is not the primary mode of action
- Male or female condom with or without spermicide
- Cervical cap, diaphragm, or sponge with spermicide
- A combination of male condom with either cervical cap, diaphragm, or sponge with spermicide (double-barrier methods)^c
- a) Contraceptive use by men or women should be consistent with local regulations regarding the use of contraceptive methods for those participating in clinical studies.
- b) Failure rate of <1% per year when used consistently and correctly. Typical use failure rates differ from those when used consistently and correctly.
- c) Male condoms must be used in addition to hormonal contraception.
- d) Considered effective, but not highly effective failure rate of ≥1% per year. Periodic abstinence (calendar, symptothermal, post-ovulation methods), withdrawal (coitus interruptus), spermicides only, and lactational amenorrhea method are not acceptable methods of contraception.
- e) Male condom and female condom should not be used together (due to risk of failure from friction).

10.4 Appendix: Contingency measures for a regional or national emergency that is declared by a governmental agency

Continuation of the study in the event of a regional or national emergency declared by a governmental agency:

A regional or national emergency declared by a governmental agency (eg, public health emergency, natural disaster, pandemic, terrorist attack) may prevent access to the clinical trial site.

Contingency procedures are suggested below and in Section 5.5, Section 6.4, Section 8, and Section 10.1.3 for an emergency that prevents access to the study site, to ensure the safety of the participants, to consider continuity of the clinical study conduct, protect trial integrity, and assist in maintaining compliance with Good Clinical Practice in Conduct of Clinical Trials Guidance. Sponsor agreement MUST be obtained prior to the implementation of these procedures for the duration of the emergency.

During the emergency, if the site will be unable to adequately follow protocol mandated procedures, alternative treatment outside the clinical trial should be proposed, and enrollment/administration of study intervention may be temporarily delayed/halted (see also Section 5.5).

Attempts should be made to perform all assessments in accordance with the approved protocol to the extent possible. In case this is not possible due to a temporary disruption caused by an emergency, focus should be given to assessments necessary to ensure the safety of participants and those important to preserving the main scientific value of the study.

Procedures to be considered in the event of a regional or national emergency declared by a governmental agency:

- If onsite visits are not possible, remote visits (eg, with home nurses, home health vendor, etc.) may be planned for the collection of possible safety and/or efficacy data
- If onsite visits are not possible visit windows may be extended for assessment of safety and/or efficacy data that cannot be obtained remotely
- Use of local clinic or laboratory locations may be allowed.

Contingencies implemented due to emergency will be documented.

10.5 Appendix: Risk-based Approach

ICH E6-R2 guideline for GCP is introducing the « risk-based approach » concept which permits to focus efforts on what is critical for a study and most specifically on Critical Data and Critical Processes. Critical data and processes are defined for the study with associated risks in the Study Risk Management Plan.

10.6 **Appendix: Abbreviations**

Ab antibody

Adverse Events AΕ

AESI Adverse events of special interest

confidence interval

AF assent form

Adverse reactions AR BLblood sampling

CI

CRF Case report form

DC diary card

DMC Data Monitoring Committee

eDC electronic diary card

ELISA enzyme-linked immunosorbent assay

ESDR early safety data review

EU European Union **FAS** Full analysis set

FDA Food and Drug Administration

FSH Follicle stimulating hormone

GCP Good Clinical Practice

GMT geometric mean titer

GPV Global Pharmacovigilance HAI hemagglutination inhibition

HAU hemagglutination units

HRT Hormonal replacement therapy

ΙB Investigator's Brochure **ICF** informed consent form

International Council for Harmonisation **ICH**

IEC Independent Ethics Committees

Trivalent inactivated influenza vaccine IIV3

IIV4 quadrivalent inactivated influenza vaccine

IM intramuscular IMP Investigational Medicinal Product

IRB Institutional Review Boards

IRT interactive response technology

LLOQ lower limit of quantitation

MA memory aid

MAAE medically attended adverse event

MDCK Madin-Darby canine kidney

MedDRA Medical Dictionary for Regulatory Activities

NA neuraminidase NI non-inferiority

NIMP Non- Investigational Medicinal Product;

PPAS Per-protocol analysis set

PSC Protein Sciences Corporation

PV pharmacovigilance

PY Person Year

QTL quality tolerance limit

RBC red blood cell

RCDC reverse cumulative distribution curve

rHA recombinant hemagglutinin

RIV3 Trivalent Recombinant Influenza Vaccine

RIV4 Quadrivalent Recombinant Influenza Vaccine

RMO Responsible Medical Officer

SAE Serious adverse events SafAS Safety Analysis Set

SAP Statistical analysis plan

SC seroconversion

SD-IIV4 standard-dose quadrivalent inactivated influenza vaccine

SMT Safety Management Team

SN seroneutralization

SoA Schedule of Activities

SUSAR suspected unexpected serious adverse reaction

TBD to be determined

USA United States of America

VAC vaccination

WHO World Health Organization

4.2.1.2.6	Serious Adverse Events	22
4.2.1.2.7	Adverse Events of Special Interest	22
4.2.2	Other Safety Endpoints	22
4.2.2.1	Pregnancy	22
4.2.2.2	Action Taken	22
4.2.2.3	Seriousness	22
4.2.2.4	Outcome	22
4.2.2.5	Causal Relationship	22
4.2.2.6	Adverse Events Leading to Study Discontinuation	
4.2.3	Immunogenicity	
4.2.3.1	Computed Values for Analysis	
4.2.3.2	Fold-rise	23
4.2.3.3	Seroconversion	
4.2.4	Derived Other Variables	
4.2.4.1	Age for Demographics	
4.2.4.2	Duration of a Participant in the Trial	
4.2.4.3	Duration of the Study	24
5	Changes in the Conduct of the Trial or Planned Analyses	25
6	Supporting Documentation	26
6.1	Appendix 1 List of Abbreviations	26
7	References	28

List of Tables

Table 1.1: Overall design	6
Table 1.2: Schedule of activities (modified compared to protocol)	
Table 2.1: Objectives and endpoints	9
Table 3.1: Descriptive statistics produced	13

List of Figures

Fie	THEO	1 1.	Graphical	atuda	dogic	gn	Q
1'1}	zurc .	l.1.	Orapilicai	Study	0C215	gn	O

1 Overall Design

The design of the study is summarized in Table 1.1.

Table 1.1: Overall design

Type of design	Parallel, multi-center
Phase	III
Control method	None
Study population	Healthy participants aged 9 to 49 years
Level and method of blinding	Open-label
Study intervention assignment method	Maximization of planned stratification of each age subgroup
Number of participants	Approximately 1334 participants (667 children and adolescents 9 to 17 years of age, and 667 adults18 to 49 years of age)
Intervention groups	Eligible participants will receive a single injection of RIV4 at D01
Total duration of study participation	Approximately 6 months
Countries	US and Europe
Use of an Independent Data Monitoring Committee, Dose Escalation Committee, or similar review group	Safety Management Team (SMT)

SAP Core Body: VAP00027

Table 1.2: Schedule of activities (modified compared to protocol)

Phase III Study, 2 Visits, 2 Phone calls, 1 Vaccination, 2 Blood Samples, 6 Months' Duration Per Participant

[figure not shown]
Visit/Contact	Collection of information in the case report form (CRF)	Visit 1	Phone Call (PC) 1*	Visit 2	PC2 6-month safety follow-up†
Study timelines (Days)		D01	D09	D29	D181
Time interval (Days)			V01 + 8D	V01 + 28D	V01 + 180D
Time windows (Days)		NA	[+2 D]	[-2, +7 D]	[+14 D]
Visit procedures:					
Informed consent	X	X			
Inclusion/exclusion criteria	X	X			

Visit/Contact	Collection of information in the case report form (CRF)	Visit 1	Phone Call (PC) 1*	Visit 2	PC2 6-month safety follow-up†
Study timelines (Days)		D01	D09	D29	D181
Time interval (Days)			V01 + 8D	V01 + 28D	V01 + 180D
Time windows (Days)		NA	[+2 D]	[-2, +7 D]	[+14 D]
Visit procedures:					
Collection of demographic data§§	X	X			
Urine pregnancy test (if applicable) ‡		X			
Collection of Medical history (Significant medical history)***	X	X			
Collection of concomitant medications	X Reportable concomitant medication	28 day	ys after vacci	nation	
History of seasonal influenza vaccination	X	X			
Contact Interactive Response Technology (IRT) system for participant number, dose number and randomization to the SN subset	X	X			
Blood sampling (BL) (5 mL)	X	BL0001**		BL0002	
Vaccination (VAC)	X	X			
Immediate surveillance (30 min)	X	X			
Collection of solicited injection site and systemic reactions	X	7 days after	vaccination		
Collection of unsolicited adverse events (AEs)	X	28 day	ys after vacci	nation	
Collection of medically attended AEs (MAAEs)	X	28 day	ys after vacci	nation	
Collection of information on serious adverse events (SAEs), including adverse events of special interest (AESIs)	X	To be	reported at a	ny time duri	ng the study

Visit/Contact	Collection of information in the case report form (CRF)	Visit 1	Phone Call (PC) 1*	Visit 2	PC2 6-month safety follow-up†
Study timelines (Days)		D01	D09	D29	D181
Time interval (Days)			V01 + 8D	V01 + 28D	V01 + 180D
Time windows (Days)		NA	[+2 D]	[-2, +7 D]	[+14 D]
Visit procedures:					
Collection of pregnancy	X	To be	reported at a	ny time duri	ng the study
End of Active Phase participation record	X			X	
Six months follow-up participant record	X				X

SAP Core Body: VAP00027

Figure 1.1: Graphical study design

BL: Blood sample VAC: vaccination PC: Phone Call

Detailed design is provided in Sections 4.1 and 1.1 of the protocol.

^{*} The investigator or an authorized designee will remind the participant or participant's parent(s)/legally acceptable representative(s) to bring back the DC/eDC at the next visit and will answer any questions.

[†] The investigator or an authorized designee will interview the participant or participant's parent(s)/legally acceptable representative(s) to collect the information recorded in the MA, and will attempt to clarify anything that is unclear ‡To be performed in menarche participants

^{**} Blood sample to be drawn before vaccination

^{§§} To comply with US Food and Drug Administration (FDA) expectations, Sponsors are to enroll participants who reflect the demographic for clinically relevant populations with regards to age, gender, race, and ethnicity (FDA. Collection of race and ethnicity data in clinical trials: Guidance for industry and Food and Drug Administration staff [Internet]. 2016. Available from: https://www.fda.gov/media/75453/download)

^{***}Including history of laboratory-confirmed influenza illness over the previous 3 influenza seasons.

2 Objectives and Endpoints

Table 2.1: Objectives and endpoints

Objectives	Endpoints
Primary	
To demonstrate the non-inferior hemagglutination inhibition (HAI) immune response of quadrivalent recombinant influenza vaccine (RIV4) for the 4 strains in participants aged 9 to 17 years vs participants aged 18 to 49 years	 Individual HAI titer 28 days after vaccination (D29) Seroconversion (SC) (titer < 10 [1/dil] at D01 and post-injection titer ≥ 40 [1/dil] at D29, or titer ≥ 10 [1/dil] at D01 and a ≥ 4-fold rise in titer [1/dil] at D29)
Key Secondary	
To summarize the HAI immune response induced by RIV4 in all participants.	 Individual-HAI titer on D01 and 28 days after vaccination (D29) Detectable HAI titer, ie, with a titer ≥ 10 (1/dil) at D01 and 28 days after vaccination (D29) Individual titer ratio: 28 days after vaccination (D29) /D01 Participants with titer ≥ 40 (1/dil) on D01 and 28 days after vaccination (D29) SC (titer < 10 [1/dil] at D01 and postinjection titer ≥ 40 (1/dil) at D29 or titer ≥ 10 (1/dil) at D01 and a ≥ 4-fold rise in titer (1/dil) at D29)
To describe the safety profile of RIV4 vaccine in all participants and by age group	 Occurrence of any unsolicited systemic adverse events (AEs) reported in the 30 minutes after vaccination Occurrence of solicited (pre-listed in the participant's diary card [DC]/electronic diary card [eDC] and case report book [CRB]) injection site reactions and systemic reactions occurring up to 8 days after vaccination Occurrence of unsolicited AEs up to 28 days after vaccination

SAP Core Body: VAP00027

	 Occurrence of medically attended adverse events (MAAEs) up to 28 days after vaccination Occurrence of serious adverse events (SAEs) (including adverse events of special interest [AESIs]) throughout the study Occurrence of AESIs throughout the study
Exploratory	
To describe the neutralizing antibody immune response in a subset of participants 1.	 Individual seroneutralization (SN) antibody (Ab) titer on D01 and 28 days after vaccination (D29) Individual SN Ab titer ratio (fold increase in post-vaccination titer relative to D01) at 28 days after vaccination (D29) Participants with SN Ab titers ≥ 20 (1/dil), ≥ 40 (1/dil), ≥ 80 (1/dil) at 28 days after vaccination (D29) Fold-increase in SN Ab titer (post/pre) ≥ 2 and ≥ 4 at 28 days after vaccination (D29) Detectable SN Ab titer (SN Ab titer ≥ 10 [1/dil]) at D01 and 28 days after vaccination (D29)

SAP Core Body: VAP00027

_

¹ At least 400 participants will be randomized to be included in the subset. The randomization of participants in the subset will be stratified to include at least 30% of children aged 9 to 11 years among children and adolescents 9 to 17 years old; and the proportion of adults aged above 35 years will be limited to 50% in the study group 18 to 49 years.

3 Statistical Considerations

3.1 Statistical Hypotheses

Primary Objective:

Statistical methodology for analyzing the 8 primary endpoints (geometric mean titers [GMTs] and SC rates).

SAP Core Body: VAP00027

Non-inferiority (NI) of the age group 9-17 years as compared to 18-49 years after vaccination of both age groups with RIV4, will be conducted for GMTs and SC rates.

Since all 8 hypotheses have to be rejected at 0.025 significance level, no formal adjustment for multiplicity is necessary.

For each strain, the NI methodology will be applied to compare the post-vaccination GMTs and the SC rates between the study groups using a 1-sided Type I error rate of 0.025 with the given individual hypothesis.

The primary analysis will be conducted in 2 steps starting with testing for NI of GMTs between the age group 9-17 years and the age group 18-49 years. If NI of GMTs based on the 4 strains is demonstrated, then NI of the SC rates will be also tested.

Step1: Geometric Mean Titers

For each of the 4 strains, the null hypothesis and the alternative hypothesis are:

H₀: $GMT_{RIV4(9-17y)} / GMT_{RIV4(18-49y)} \le 0.667$

 $H_A: GMT_{RIV4(9-17y)}/GMT_{RIV4(18-49y)} > 0.667$

or equivalently,

 H_0 : log_{10} (GMT_{RIV4(9-17y)}) - log_{10} (GMT_{RIV4(18-49y)}) $\leq log_{10}$ (0.667)

 H_A : $log_{10} (GMT_{RIV4(9-17y)}) - log_{10} (GMT_{RIV4(18-49y)}) > log_{10} (0.667)$

For the separately considered GMT hypotheses, if the null hypothesis is rejected, then the alternative hypothesis of NI is supported.

All 4 strains must show NI of GMTs to consider that GMTs have demonstrated NI.

Step 2: Seroconversion Rates

For each of the 4 strains, the null hypothesis and the alternative hypothesis are:

H₀: $P_{RIV4(9-17y)} - P_{RIV4(18-49y)} \le -10\%$

H_A: $P_{RIV4(9-17y)} - P_{RIV4(18-49y)} > -10\%$

For the separately considered seroconversion hypotheses, if the null hypothesis is rejected, then the alternative hypothesis of NI is supported.

All 4 strains must demonstrate NI of the SC rates to consider that SC rates have demonstrated NI.

Secondary Objectives:

There are no statistical hypotheses to be tested in the secondary objectives.

3.2 Sample Size Determination

A total of approximately 1200 evaluable participants 9 to 49 years of age (600 children and adolescents 9 to 17 years of age [approximately 30% children 9 to 11 years of age] and 600 adults 18 to 49 years of age) will be assessed.

SAP Core Body: VAP00027

Assuming the same GMT for each strain in the age groups (9 to 17 years vs. 18 to 49 years) compared, and a standard deviation of log₁₀ titers of 0.6 with a NI margin of 1.5; NI for GMTs would be demonstrated with a power of at least 99.6%.

Assuming in each vaccine group the same expected SC rates (0.7, 0.5, 0.6, 0.5) for each of the 4 strains (A/H1N1, A/H3N2, B/Yamagata and B/Victoria), based on conservative estimates from historical data, and a NI margin of 10%, the NI for SC rate can be demonstrated with a study power of approximately 80.10% (96.66%, 93.70%, 94.38% and 93.70% for each strain, respectively).

Hence, the overall study power is estimated to be 80.0% (80.0% = 99.6%[GMTs] x 80.10%[SC rate]).

As shown above, to keep the overall study power of 80%, the sample size was increased accordingly, to have an overall type II error <20% for the 8 NI tests.

Assuming an attrition rate of approximately 10% in this age group, a total of approximately 1334 participants 9 to 49 years of age will be enrolled.

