The number of participants enrolled and their age at enrollment, sex, race, and ethnic origin will be summarized for each group, as well as the number and description of protocol deviations. In general, categorical variables will be summarized and presented by frequency counts, percentages, and CIs. The 95% CIs of point estimates will be calculated using the normal approximation for quantitative data and the exact binomial distribution (Clopper-Pearson method) for percentages. For GMTs, 95% CIs of point estimates will be calculated using the normal approximation of log-transformed titers.

Primary endpoints:

The primary objective includes 8 endpoints (GMTs and seroconversion (SC) rates for each of the 4 strains).

For each strain, the non-inferiority (NI) methodology will be applied to compare the post-vaccination GMTs and the SC rates between the groups using a 1-sided Type I error rate of 0.025 with the given individual hypothesis.

The primary analysis will be conducted in 2 steps, starting with testing for NI of GMTs between the study groups. If NI of GMTs based on the 4 strains is demonstrated, then NI for SC will also be tested.

Since all 8 hypotheses have to be rejected at 0.025 significance level, no formal adjustment for multiplicity is necessary.

To keep the study power of 80%, the sample size was increased accordingly, to have an overall Type II error <20% for the 8 NI tests.

Secondary endpoints (immunogenicity):

Immunogenicity parameters by HAI measurement method will be described by study group with 95% confidence intervals (CIs).

Reverse cumulative distribution curves (RCDCs) of pre-vaccination titer at D01 and post-vaccination titer at D29 will be generated for each study group.

Subgroup analyses will be performed; in particular, immunogenicity will be described according to age subgroups, sex, race, previous influenza vaccination status, and baseline seropositivity status, as appropriate according to number of participants in the respective subgroups.

Secondary endpoints (safety):

For the main safety parameters, 95% CIs of point estimates will be calculated using exact binomial method (Clopper-Pearson method) for single proportions and using the normal approximation for quantitative data.

Analysis will be conducted for each study group.

Data Monitoring/Other Committee:

No independent Data Monitoring Committee (DMC) is planned.

[figure not shown]

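### The printed overall power is a false product: 99.6% × 80.10% is 79.8%, not 80.0%, so a type II error below 20% is not shown (minor erratum)

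*SAP*

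**What the plan says.** SAP 3.2 and Protocol 9.2 carry the same sample-size text. It plans on "A total of approximately 1200 evaluable participants 9 to 49 years of age", 600 in each age group. For the GMTs it assumes equal true values and an SD of log10 titers of 0.6, and states that "NI for GMTs would be demonstrated with a power of at least 99.6" per cent. For seroconversion it assumes equal rates of 0.7, 0.5, 0.6 and 0.5 and a 10-point margin. It gives per-strain powers of 96.66%, 93.70%, 94.38% and 93.70%, and a joint power of approximately 80.10%.

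The two factors are then multiplied: "Hence, the overall study power is estimated to be 80.0% (80.0% = 99.6%[GMTs] x 80.10%[SC rate".

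The following sentence relies on that result. It opens "As shown above, to keep the overall study power of 80%, the sample size was increased accordingly" and gives the purpose as "to have an overall type II error <20% for the 8 NI tests". The Protocol Synopsis (1.1) repeats the aim, "to have an overall Type II error <20% for the 8 NI tests", without any calculation.

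**The concern.** The equation can be checked by hand and does not hold. It is printed to one decimal, so 80.0% cannot be read as a loose rounding of 79.8%. The correct product also falls on the other side of the 80% threshold, so the sentence that cites the calculation as showing a type II error below 20% cites one that gives slightly more than 20%.

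Little is at stake. The primary objective succeeds only if all eight tests succeed, so the joint power is the right figure to report, and it should follow from the derivation given for it. No design decision turns on the difference. The practical risk is that a false equation is copied into later documents.

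**Working it through.** **Inputs, all from SAP 3.1, 3.2 and 3.4.2 (the same figures are in Protocol 9.1, 9.2 and 9.4.2)**
- Error rate: "using a 1-sided Type I error rate of 0.025 with the given individual hypothesis"
- 600 evaluable per group
- GMT: SD 0.6 on the log10 scale, margin 1.5-fold, true ratio 1
- Seroconversion: rates 0.7, 0.5, 0.6, 0.5 in both groups, margin 10 points, Wilson score (Newcombe) interval without continuity correction

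**1. The printed product**
- 0.996 × 0.8010 = 0.7978, i.e. 79.8%. Type II error = 1 − 0.7978 = 0.2022, i.e. 20.2%.
- Lowest values that round to the printed factors: 0.9955 × 0.80095 = 0.7973.
- Highest: 0.9965 × 0.80105 = 0.7982.
- Rounding of the factors therefore cannot produce 80.0%.

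**2. Are the two factors themselves right?**

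*GMT.* Per-strain power = Φ(log10(1.5) / (0.6 × √(2/600)) − 1.96) = Φ(0.17609 / 0.03464 − 1.96) = 0.99911. For four independent strains, 0.99911⁴ = 0.99643. With the noncentral t distribution the four-strain figure is 0.99638. With the margin coded as 0.667 it is 0.99635 (normal) or 0.99630 (t). The printed 99.6% is therefore the four-strain product.

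*Seroconversion.* The exact binomial probability that the Wilson/Newcombe lower limit exceeds −10%, at 600 per group, is:

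| Strain | Rate | Recomputed | Printed |
|---|---|---|---|
| A/H1N1 | 0.7 | 96.66% | 96.66% |
| A/H3N2 | 0.5 | 93.70% | 93.70% |
| B/Yamagata | 0.6 | 94.38% | 94.38% |
| B/Victoria | 0.5 | 93.70% | 93.70% |
| Product | | 80.09% | 80.10% |

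Both factors reproduce. Only the last multiplication fails.

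**3. Overall power from unrounded components**
- 0.80094 × 0.99643 = 0.7981, i.e. 79.8%.
- Coding the margin as 1.5 or 0.667, and using the normal or t distribution, gives 79.80% to 79.81%.
- An unpooled normal approximation for seroconversion gives 79.06%.
- None of these gives 80.0% at 600 per group.

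**4. Does reading 99.6% as a floor rescue the equation?**
- To round to 80.0%, the GMT factor must be at least 0.7995 / 0.8010 = 99.81%.
- To reach 80.00%, it must be at least 0.8000 / 0.8010 = 99.88%.
- The stated inputs give 99.64% for four strains, so it does not. The single-strain value would (0.99911 × 0.8010 = 0.8003), but the claim covers all four strains.

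**5. The gap in participants**
- Recomputing both factors at each n gives 79.96% at 602 per group and 80.01% at 603.
- Holding the GMT factor at the printed 99.6%, 80.0% is first reached at 609 per group.
- The equivalent is therefore 3 to 9 more evaluable participants per group, depending on the convention.

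**The case against.** The strongest reply is that the error has no consequence. The discrepancy is 0.2 points in a figure described as an estimate, built on approximate inputs, and at whole-percent precision 79.8% is 80%. SAP section 5 reports the last adult enrolled on 5 January 2023 and the last 9-to-17-year-old on 28 April 2023, so no sample-size decision remains. All of this stands, and it is why the point is only an erratum. It does not make the printed equation true.

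A second reply is that true power may well be 80% or more. Seroconversion is derived from the same D29 HAI titer that enters the GMT (SAP 4.2.3.2 and 4.2.3.3), so the tests are probably positively correlated. With the two printed factors held fixed, joint power is 79.8% under independence and at most 80.1% if seroconversion success always implies GMT success. Positive correlation among strains would raise the 80.10% factor itself. This also stands, so the below-20% claim cannot be called false. But the documents multiply the powers, give no correlation and do not make this argument. The claim is unsupported by the derivation it cites.

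A third reply is that the below-20% phrase states a design target, which an arithmetic correction should leave alone. That reading fits the Synopsis, where no calculation is printed. It is harder to sustain in SAP 3.2 and Protocol 9.2, where the sentence points back to the calculation as having shown the result.

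**Conclusion.** The point holds at the lowest severity. By the sections' own product rule, overall power is 79.8% rather than 80.0%, and type II error is 20.2% rather than below 20%. This rests on the stated inputs (600 evaluable per group, SD 0.6, equal true responses in the two age groups, the stated seroconversion rates) and on independence of the eight tests, which the multiplication implies but the text does not state. The component powers are sound. The trial is not shown to be underpowered, and the Synopsis contains no arithmetic error.

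**What to change.** In SAP 3.2 and Protocol 9.2, replace the power equation with wording such as: *Treating the eight tests as independent, overall power is about 80% (99.6% for GMTs × 80.10% for SC rates = 79.8%); positive correlation among the endpoints would raise it.* In the sentence that follows, in both sections, change the type II error from below 20% to approximately 20%. The Synopsis can be aligned for consistency, but this is optional.

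The cost is two text edits in each document, plus the optional one, at the next revision. Enrolment, margins, tests and analyses do not change.
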